#### 2.5.1.2 Overall Survival (OS)

For patients who have died, overall survival is calculated in months from the day of randomization to date of death. Otherwise, survival is censored at the last day the patient is known alive (LKA).

$$\text{OS Time (months)} = ((\text{date of death or LKA} - \text{date of randomization}) + 1) / 30.4375$$

#### 2.5.1.3 Response Rate

Response will be evaluated in this study using the revised international RECIST Criteria (1.1)

All patients who have received at least one dose of therapy and have their disease re-evaluated will be considered evaluable for response (exceptions will be those who exhibit objective disease progression prior to the end of cycle 1 who will also be considered evaluable). Patients on therapy for at least this period and who meet the other listed criteria will have their response classified as CR, PR, SD and PD. Patients with non measurable disease will only have a best response of either CR or 'Non CR/Non PD'.

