## 2 Methods and Analyses

### 2.1 Analyses Samples

Patients were randomized to the following two treatment arms:

- Arm 1: Palbociclib 100 mg po daily.
- Arm 2: Palbociclib 125 mg po daily 3 out of 4 weeks

The study populations for this analysis will include both the intention to treat (ITT) population and the as treated population.

Analysis of pretreatment characteristics and all efficacy outcomes such as PFS and OS, will be based on the ITT population. The efficacy data set consists of all patients regardless of actual treatment.

Those who received at least one dose of protocol therapy (i.e. the as treated population) will form the basis of the safety analyses. The response analyses will include patients with measurable disease or those with non measurable disease who experience a CR. QOL analyses will include all patients who completed at least one QOL assessment (either baseline or follow-up).

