#### 2.5.2.3 Response Rate and Clinical Benefit Rate

Response rates (percentages of CR/PR as best response) will be reported by treated arms for patients evaluable for response.

Clinical benefit rates (percentages of CR/PR/SD as best response) will be reported by treated arms for patients evaluable for response.

Response rates and clinical benefit rates will be compared between two arms using the Cochran-Mantel-Haenszel test adjusting for stratification factors at randomization (Table 16).

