Other condition or circumstance			
Patients who were censored			
Reason Censored			
Still Alive			
Withdrawal of Consent			

*Table 16: Response to Treatment*

	Number of Patients (%)		
	Data set: All treated patients with measurable disease		
	Palbociclib 100mg N = ***	Palbociclib 125mg N = ***	
Response to treatment			
CR	XX (%)	XX (%)	XX (%)
PR			
SD			
PD			

\*Stratification CMH test p-value for response rate:  $(CR+PR)/(CR+PR+SD+PD)$

\*\*Stratification CMH test p-value for clinical benefit rate:  $(CR+PR+SD)/(CR+PR+SD+PD)$

*Table 17: Duration of Response*

	Number of Patients (%)		
	Data set: All patients with CR/PR		
	Palbociclib 100mg N = ***	Palbociclib 125mg N = ***	Stratified p-value from log rank test
Duration of response			
Median	XX	XX	p-value =
Min	XX	XX	-
Max	XX	XX	-
Q1	XX	XX	-
Q3	XX	XX	-

*Table 18: Dose information*

Data set: All treated Patients: Cumulative dose (mg)			
	Number of patients		
	Palbociclib 100mg N = ***	Palbociclib 125mg N = ***	Total N = ***
Median	***	***	***
Min	**	**	**
Max	**	**	**
Q1			
Q3			

Cumulative dose (mg)

n

Mean

Std

Median

Min

Max

Q1

Q3

*Similar tables for*

*Daily dose(mg),*

*Dose intensity (mg/week)*

*Relative dose intensity (percent)*

*Cycle 1 and 2 dose intensity (mg/week)*

*Cycle 1 and 2 relative dose intensity (percent)*

90% or more dose intensity: N and percent

Data set: All treated Patients			
90% or more dose intensity: N and percent	Number of patients		
	Palbociclib 100mg N = ***	Palbociclib 125mg N = ***	Total N = ***
No	***	***	***
Yes	**	**	**

Cycle 1 and 2 90% or more dose intensity: N and percent

Data set: All treated Patients			
Cycle 1 and 2 90% or more dose intensity: N and percent	Number of patients		
	Palbociclib 100mg N = ***	Palbociclib 125mg N = ***	Total N = ***
No	***	***	***
Yes	**	**	**

*Table 19: Dose modifications*

Data set: All treated Patients			
At least one dose modification	Number of patients		
	Palbociclib 100mg N = ***	Palbociclib 125mg N = ***	Total N = ***
Yes	**	**	**
Reason of dose modifications Reason 1 Reason 2 ...			

Data set: All treated Patients			
At least done dose Reduction	Number of patients		
	Palbociclib 100mg N = ***	Palbociclib 125mg N = ***	Total N = ***
Yes	**	**	**
Reason of dose reduction Reason 1 Reason 2 ...			

Data set: All treated Patients			
Patients with dose discontinuation	Number of patients		
	Palbociclib 100mg N = ***	Palbociclib 125mg N = ***	Total N = ***
Yes	**	**	**
Reason of dose discontinuation			

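### The SAP gives three different denominators for response and clinical benefit, and the one it uses drops patients who are never re-evaluated and runs the between-arm test without them

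*SAP*

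**What the plan says.** Four places in the SAP bear on who is counted.

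- **Section 2.1** bases efficacy outcomes in general on ITT: "The efficacy data set consists of all patients regardless of actual treatment". It then gives response its own set: patients with measurable disease, plus those with non-measurable disease who reach CR. Neither dosing nor re-evaluation is required there.
- **Section 2.5.1.3** adds both conditions: "All patients who have received at least one dose of therapy and have their disease re-evaluated will be considered evaluable for response". The one carve-out is "exceptions will be those who exhibit objective disease progression prior to the end of cycle 1 who will also be considered evaluable".
- **Section 2.5.2.3** adopts the evaluable set for both endpoints. For response: "Response rates (percentages of CR/PR as best response) will be reported by treated arms for patients evaluable for response". For clinical benefit: "Clinical benefit rates (percentages of CR/PR/SD as best response) will be reported by treated arms for patients evaluable for response". It then tests on it: "Response rates and clinical benefit rates will be compared between two arms using the Cochran-Mantel-Haenszel test adjusting for stratification factors at randomization".
- **Table 16** is headed as covering treated patients who have measurable disease, with no re-evaluation condition. Its footnotes define the tested response rate as ("CR+PR)/(CR+PR+SD+PD"), and the clinical benefit rate has the same denominator. The rows are CR, PR, SD and PD only. There is no row for patients not evaluated.

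**The concern.** There are two problems, and the first holds whatever the data show.

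First, the three descriptions of the response set differ. The column totals in Table 16 (all treated with measurable disease) and the rates tested in its footnotes (only those with an assigned response) can refer to different patients. Two analysts could follow the SAP faithfully and report different rates.

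Second, having a re-evaluation is a post-randomization event that treatment can influence. Conditioning on it means the CMH test no longer compares the groups as randomized. A patient with measurable disease who dies without documented progression before any re-evaluation has plainly not responded, yet the evaluable-only rule removes that patient instead of counting a failure. The arm that loses more such patients gets the smaller denominator and, for the same number of responders, the higher rate.

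**Working it through.** **Who is counted under each description (measurable disease at baseline)**

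| Patient | Section 2.1 | Sections 2.5.1.3 and 2.5.2.3 | Table 16 header | Table 16 footnote rates |
|---|---|---|---|---|
| Never dosed | in | out | out | out |
| Dosed, objective progression before end of cycle 1 | in | in | in | in (PD) |
| Dosed, dies without objective progression, no re-evaluation | in | out | in | out (no category) |
| Dosed, stops, never re-evaluated, no objective progression | in | out | in | out (no category) |
| Dosed, stops, re-evaluated later | in | in | in | in |

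The last line follows the evaluability sentence in 2.5.1.3, which does not require the re-evaluation to be on treatment. The next sentence there limits classification to patients on therapy for a period that is not clearly identified. On one reading this would also exclude some early stoppers who are scanned later.

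**Size of the effect**

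The SAP states no response rate, clinical benefit rate or non-evaluable share, so there is no figure of its own to reproduce on this point. The only SAP input is the planned 90 patients per arm (section 1.2). The rest is assumed: all 90 have measurable disease, both arms have the same number of responders and of patients with benefit, and m patients in an arm are unassessed.

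- Rate with all patients counted: r / 90
- Rate by the SAP rule: r / (90 − m)
- Spurious difference, arm B minus arm A: r / (90 − mB) − r / (90 − mA)

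Nominal shares of 2% vs 5%, 2% vs 10% and 5% vs 15%, rounded to whole patients, give 2 vs 4, 2 vs 9 and 4 vs 14.

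| Rate with all counted (both arms) | 2 vs 4 out | 2 vs 9 out | 4 vs 14 out | 4 vs 4 out |
|---|---|---|---|---|
| Response 18/90 = 20% | 20.5 vs 20.9 (+0.5) | 20.5 vs 22.2 (+1.8) | 20.9 vs 23.7 (+2.8) | 20.9 vs 20.9 (0) |
| Response 27/90 = 30% | 30.7 vs 31.4 (+0.7) | 30.7 vs 33.3 (+2.7) | 31.4 vs 35.5 (+4.1) | 31.4 vs 31.4 (0) |
| Benefit 54/90 = 60% | 61.4 vs 62.8 (+1.4) | 61.4 vs 66.7 (+5.3) | 62.8 vs 71.1 (+8.3) | 62.8 vs 62.8 (0) |
| Benefit 63/90 = 70% | 71.6 vs 73.3 (+1.7) | 71.6 vs 77.8 (+6.2) | 73.3 vs 82.9 (+9.6) | 73.3 vs 73.3 (0) |

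Differences are taken before rounding. Rounding to whole patients matters a little: 4 of 90 is 4.4% and 14 of 90 is 15.6%. With exact shares the ends of the range are 0.20/0.95 − 0.20/0.98 = 0.6 to 0.30/0.85 − 0.30/0.95 = 3.7 points for response, and 0.60/0.95 − 0.60/0.98 = 1.9 to 0.70/0.85 − 0.70/0.95 = 8.7 points for clinical benefit.

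The order of the arms can also reverse: 27/90 vs 26/90 (30.0% vs 28.9%) becomes 27/88 vs 26/81 (30.7% vs 32.1%).

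**Effect on the test**

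At the largest example, using an unadjusted pooled z:

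- Response: p = 54/162 = 0.333, SE = √(0.333 × 0.667 × (1/86 + 1/76)) = 0.074, z = 0.041/0.074 = 0.56.
- Clinical benefit: p = 126/162 = 0.778, SE = √(0.778 × 0.222 × (1/86 + 1/76)) = 0.065, z = 0.096/0.065 = 1.47.

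Neither reaches 1.96, the two-sided 5% value that applies under section 2.3. In these examples the artefact alone would not produce significance, but it would add to or offset a real difference.

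**The case against.** Several stronger readings are tempting, and the SAP does not support them.

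- **That 2.5.1.3 overrides an ITT promise for response.** A reader might infer this from the general efficacy sentence in 2.1. But 2.1 itself takes response off full ITT, by measurability. The conflict is between that set and the re-evaluation condition added later.
- **That the less tolerable regimen will look more active.** The SAP lists safety and tolerability as a secondary objective (section 1.1) but states no expected difference and no direction. The bias needs unequal losses, and which arm would gain is unknown.
- **That everyone who stops for toxicity before a first scan is dropped.** The evaluability sentence does not say so: a patient scanned after stopping can remain evaluable, and early objective progressors stay in.
- **That the 10% dropout in section 1.2 measures the loss.** That figure inflates the PFS sample size over accrual and follow-up. It is not a rate of missing first re-evaluations, and a patient who drops out after one scan is evaluable.

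It can fairly be added that these are secondary endpoints in a trial designed to estimate a PFS hazard ratio, and that PFS is analysed by ITT with death as an event. The SAP also plans a CONSORT diagram, treatment received (Table 3), off-treatment reasons (Table 23) and deaths within 30 days of last treatment (Table 24), so many early losses will be visible. What this leaves standing is the inconsistency, and the fact that none of those displays corrects the rates or the CMH test.

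**Conclusion.** The point holds as a secondary-endpoint issue that should be fixed. The SAP states three response sets, and the rule it applies to both rates and to the CMH test excludes patients with measurable disease who are never dosed or never re-evaluated, unless they show early objective progression. Both rates are then inflated. If such losses differ by arm, the comparison is biased toward the arm that loses more.

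The size rests wholly on assumed shares. For 2 vs 4 up to 4 vs 14 unassessed of 90 (roughly 2% vs 5% up to 5% vs 15%), with equal true rates (response 20–30%, benefit 60–70%), the spurious difference is about 0.5 to 4 points for response and 1.4 to 10 points for clinical benefit. It is zero when losses are equal. The SAP does not show that a bias of this size will occur, or in which direction.

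**What to change.** Change sections 2.1, 2.5.1.3, 2.5.2.3 and Table 16 together, so that one denominator applies throughout:

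- Make all randomized patients with measurable disease at baseline the primary denominator for response and clinical benefit.
- Add a row to Table 16 for patients not evaluable or not assessed, by arm and with the reason (not treated, early death, toxicity, withdrawal). Count them as no response and no clinical benefit.
- Run the stratified CMH test on this set, and make the table header and footnote denominators agree with it.
- Report evaluable-only rates as a sensitivity analysis, and patients with non-measurable disease separately. Section 2.1 must be amended too; otherwise its inclusion of non-measurable CRs would conflict with the new denominator.

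The cost is SAP wording, one table row and a little more analysis; reported rates will be slightly lower. The SAP is dated 2018-08-08, after the clinical cut-off of April 16, 2018, so the change of primary denominator should be recorded as a dated amendment, with both sets of rates shown.

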#### 2.5.1.5: Clinical Benefit Rate

Clinical benefit includes patients with documented CR, RP or SD for those with measurable disease and CR for with non measurable disease.

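### The SAP leaves no best-response category for progression in non-measurable disease, and it defines three different populations for the response and clinical benefit rates

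*SAP*

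**What the plan says.** **Categories.** Section 2.5.1.3 defines who is evaluable: "All patients who have received at least one dose of therapy and have their disease re-evaluated will be considered evaluable for response". It then adds early progressors: "exceptions will be those who exhibit objective disease progression prior to the end of cycle 1 who will also be considered evaluable". Neither clause requires measurable disease. The section goes on to list CR, PR, SD and PD as the classes, and closes with the restriction: "Patients with non measurable disease will only have a best response of either CR or 'Non CR/Non PD".

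**Populations.** The SAP says in several places who enters the response analyses:

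- Section 2.1: "The response analyses will include patients with measurable disease or those with non measurable disease who experience a CR".
- Section 2.5.2.3: "Response rates (percentages of CR/PR as best response) will be reported by treated arms for patients evaluable for response". Clinical benefit rates have the same population, and both rates are compared between arms with a stratified Cochran-Mantel-Haenszel (CMH) test.
- Table 16: the data set is treated patients whose disease is measurable. The clinical benefit rate is "CR+PR+SD)/(CR+PR+SD+PD", with no term for Non CR/Non PD.

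**Numerator.** Section 2.5.1.5 counts CR, PR or SD as clinical benefit in measurable disease, and "CR for with non measurable disease".

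**The concern.** There are two separate defects.

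First, the category rule is wrong as written. A patient with non-measurable disease who progresses at or before the first re-evaluation is evaluable, but may only be recorded as CR or Non CR/Non PD. Both labels would be false, and Non CR/Non PD would contradict the progression event that section 2.5.1.1 counts for the same patient. The programmer must mislabel the patient, leave the field empty or improvise.

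Second, the denominator of two secondary endpoints depends on which section is followed. Under section 2.1 a patient with non-measurable disease is admitted because of the result, namely a CR. Together with section 2.5.1.5, that patient counts as a success, while patients with non-measurable disease and Non CR/Non PD or PD leave the denominator.

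Response rate and clinical benefit rate are both listed as secondary objectives in section 1.1 and are both tested between arms. An undefined denominator leaves the reported rate open to choice.

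**Working it through.** The SAP states no figure on this point, so there is none to reproduce. The check sets the definitions side by side and then counts patients under each.

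**Who is in the denominator**

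| Patient | 2.5.1.3 with 2.5.2.3 | 2.1 | Table 16 |
|---|---|---|---|
| Measurable disease | in | in | in |
| Non-measurable, CR | in | in | out |
| Non-measurable, Non CR/Non PD | in | out | out |
| Non-measurable, PD | in, but without a category | out | out |

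The three columns differ, and only the section 2.1 column splits non-measurable disease by outcome.

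**Inputs for the illustration**

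- 90 patients per arm: SAP section 1.2. All are taken as evaluable.
- Non-measurable share 20%, so 18 non-measurable and 72 measurable: assumed.
- Non-measurable outcomes 1 CR, 13 Non CR/Non PD, 4 PD: assumed.
- Measurable disease, clinical benefit 75% (54 of 72) and response 25% (18 of 72): assumed.

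**Clinical benefit rate**

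- Section 2.1: (54 + 1) / (72 + 1) = 55/73 = 75.3%
- Table 16: 54/72 = 75.0%
- All evaluable: (54 + 1) / 90 = 55/90 = 61.1%

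**Response rate**

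- Section 2.1: (18 + 1) / 73 = 19/73 = 26.0%
- Table 16: 18/72 = 25.0%
- All evaluable: 19/90 = 21.1%

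**Range.** With the same assumed rates in measurable disease, about 3% CR in non-measurable disease, and whole patients:

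| Assumed non-measurable share | 2.1 | Table 16 | All evaluable |
|---|---|---|---|
| 10% (9 of 90) | 61/81 = 75.3% | 61/81 = 75.3% | 61/90 = 67.8% |
| 20% (18 of 90) | 55/73 = 75.3% | 54/72 = 75.0% | 55/90 = 61.1% |
| 30% (27 of 90) | 48/64 = 75.0% | 47/63 = 74.6% | 48/90 = 53.3% |
| 40% (36 of 90) | 41/55 = 74.5% | 40/54 = 74.1% | 41/90 = 45.6% |

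**Patients without a category.** Take the SAP's 10-month median PFS (section 1.2), exponential times, and a first assessment at 8 to 12 weeks (assumed). The proportion with an event is 1 − exp(−(ln 2 / 10) × t), with t in months: 12.0% at 8 weeks and 17.4% at 12 weeks. For an assumed 18 to 27 non-measurable patients per arm, this gives 18 × 0.120 = 2.2 to 27 × 0.174 = 4.7 patients. PFS events include deaths, so not all of these would be PD as best response. With a non-measurable share of 10–40% and PD in 10–30% of those patients, the count runs from 1 to 11 per arm.

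**Does the missing PD label move a rate?** Under section 2.1 the denominator is 73 with or without a PD category, and under Table 16 it is 72 either way. The label matters only if the evaluable population of section 2.5.2.3 is combined with the Table 16 formula. Clinical benefit is then 55/73 = 75.3% without the category and 55/(73 + 4) = 55/77 = 71.4% with it.

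**The case against.** The strongest reply is that the closing sentence of section 2.5.1.3 is only loosely worded. The section places response under RECIST 1.1, and the sentence before lists PD without limiting it to measurable disease. The restriction may have been meant only to replace PR and SD with Non CR/Non PD. That is a plausible intention, but the word *only* excludes PD, so the text still needs correcting.

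A reader might also infer that the missing category is what removes progressors from the denominators. The documents do not support this. Section 2.1 and the Table 16 data set exclude these patients whatever their label, along with the Non CR/Non PD patients. The evaluable population of section 2.5.2.3 keeps them in, unlabelled. Only the mixed reading shown in the working makes the label matter, and no section prescribes that reading.

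Nor does every reading bias the rates upward. Table 16 leaves out non-measurable CRs as well, so it has no asymmetry. The all-evaluable reading lowers clinical benefit, because section 2.5.1.5 credits non-measurable disease with CR alone. The upward selection comes from section 2.1. Against measurable disease alone it is small: 75.3% versus 75.0% in the illustration.

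It also stands that these are secondary endpoints, that the same rules apply to both arms, and that progression in non-measurable disease still counts in PFS and appears in Table 12 for all randomized patients.

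**Conclusion.** The concern holds on two counts. The category rule in section 2.5.1.3 contradicts the evaluability rule in the same section for patients with non-measurable disease who progress. In addition, the SAP gives three response populations that cannot all apply, and the one in section 2.1 admits non-measurable patients on outcome, which biases both rates upward.

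The conflict of populations is the larger matter. At an assumed 20% non-measurable share, clinical benefit differs by 75.3 − 61.1 = 14.2 percentage points between section 2.1 and all evaluable patients, and response by 26.0 − 21.1 = 4.9 points. Most of this gap comes from whether the 17 non-measurable patients without a CR are counted, not from the missing PD category. All sizes rest on assumed shares and rates, since the SAP gives none. The contradictions themselves rest on the text alone. The point should be corrected, but it does not touch the primary analysis.

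**What to change.** 1. Section 2.5.1.3: allow CR, Non CR/Non PD, PD and not evaluable as best response in non-measurable disease.
2. Section 2.1: delete the clause that admits patients with non-measurable disease only if they have a CR.
3. Sections 2.1, 2.5.1.5, 2.5.2.3 and Table 16: state that the main response rate, the main clinical benefit rate and their CMH tests use patients with measurable disease.
4. Table 16: add a separate panel for non-measurable disease showing the categories in item 1, with all evaluable such patients in the denominator.

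The cost is SAP wording and one table panel. The main rates lose the few CRs in non-measurable disease, which then appear in the new panel. No new data are needed, and PFS does not change.

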#### 2.5.1.4 Response Duration

For patients with documented CR or PR, duration of response is calculated from the time of CR or PR (whichever is first recorded) until the first date that recurrent or progressive disease is objectively documented or death occurs. If a patient has not progressed or died at the time of the final analysis, duration of response will be censored on the date of the last disease assessment.

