### 2.5 Efficacy

#### 2.5.1 Definitions and Variables

##### 2.5.1.1 Progression-free Survival (PFS)

The primary endpoint is progression free survival (PFS) defined as time from randomization to progression or death from any cause. Disease progression will be investigator assessed using the RECIST 1.1 criteria. If a patient has not progressed or died at the time of final analysis, PFS will be censored on the date of the last disease assessment. If a patient received anti-cancer RT treatment, PFS will be censored at the date of anti-cancer treatment.

PFS Time (months) =

((date of PFS event or last disease assessment date - date of randomization) + 1) / 30.4375

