#### 2.5.2.4 Duration of Response

Duration of response (median, Q1, Q3, min, max) will be reported by treated arms for patients with CR/PR. The difference in duration of response between the two treatment arms will be tested using the log-rank test adjusting for stratification factors at randomization (Table 17).

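### Duration of response runs on through anti-cancer radiotherapy, where PFS is censored, so a responder's duration can exceed her own PFS time

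*SAP*

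**What the plan says.** PFS (SAP 2.5.1.1) runs from randomization to progression or death and is otherwise censored at the last disease assessment. One further rule follows: "If a patient received anti-cancer RT treatment, PFS will be censored at the date of anti-cancer treatment". The first half of that sentence names RT; the second half names anti-cancer treatment in general.

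Duration of response (SAP 2.5.1.4) starts when CR or PR is first recorded and runs "until the first date that recurrent or progressive disease is objectively documented or death occurs". For a patient with neither event at the final analysis, "duration of response will be censored on the date of the last disease assessment". RT and other anti-cancer treatment are not mentioned.

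Duration is then used for a formal comparison (SAP 2.5.2.4): "The difference in duration of response between the two treatment arms will be tested using the log-rank test adjusting for stratification factors at randomization". The p-value goes into Table 17.

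**The concern.** The two sections share the same end events and almost the same rule for patients without an event, but only PFS stops at RT. No reason for the difference is given. Because 2.5.1.4 sets out both its end event and its censoring rule, this is a mismatch between two stated rules and not a detail left to the protocol.

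For a responder irradiated before progression, the same later progression is left out of the primary endpoint and counted as an event for duration of response. Any disease control after RT is then included in the reported duration. A reader who compares Table 17 with the PFS results could find durations of response longer than the same patients' PFS times. That cannot happen when both endpoints stop at the same point, because response cannot start before randomization.

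**Working it through.** **Design figures.** No SAP figure is in dispute. The interval factors in SAP 1.2 (58 events per arm, 90% interval) reproduce: exp(±1.645 × √(1/58 + 1/58)) = 1.357 and 0.737, against the stated 1.36 and 0.74. They concern the PFS hazard ratio and do not change.

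**Rules side by side.**

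| | PFS (2.5.1.1) | Duration of response (2.5.1.4) |
|---|---|---|
| Start | Randomization | First CR or PR |
| Event | Progression or death | Progression or death |
| No event | Censored at last assessment | Censored at last assessment |
| Anti-cancer RT first | Censored at that date | No rule; follow-up continues |

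**When duration exceeds PFS time.** Let R, T and P be the times from randomization to response, RT and progression, with R < T < P. PFS is censored at T. Duration as written is an event at P − R. Duration exceeds PFS time whenever P − R > T, that is, P > R + T.

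**Example in months (illustrative dates).** R = 3, T = 6, P = 14.
- PFS: censored at 6.
- Duration as written: 14 − 3 = 11, an event.
- Duration under the PFS rule: 6 − 3 = 3, censored.
- Check: 14 > 3 + 6 = 9, so duration exceeds PFS time.

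**Example in days (illustrative dates), on the SAP's time scale.** The PFS formula is "date of PFS event or last disease assessment date - date of randomization) + 1) / 30.4375". The SAP gives no formula for duration, so the added day and the divisor are borrowed from PFS. Take response on day 84, RT on day 168 and progression on day 336.
- PFS: (168 + 1)/30.4375 = 5.55 months, censored.
- Duration as written: (336 − 84 + 1)/30.4375 = 8.31 months, an event.
- Duration under the PFS rule: (168 − 84 + 1)/30.4375 = 2.79 months, censored.

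**Size of the effect on an arm's median duration.** The SAP gives no response duration and no RT frequency, so this rests on assumptions: exponential duration with a true median of 12 months, a 24-month horizon, and RT timing unrelated to the risk of progression. Each scenario used 200,000 simulated responders.

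| Responders with RT before progression | Effect of RT on later hazard | Median as written | Median if censored at RT |
|---|---|---|---|
| about 5% | none | 11.94 | 11.94 |
| about 5% | halved | 12.19 | 12.01 |
| about 11% | none | 12.00 | 11.98 |
| about 11% | halved | 12.34 | 11.99 |
| about 22% | none | 12.02 | 12.04 |
| about 22% | halved | 12.73 | 12.01 |

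If RT has no effect, the two rules agree within simulation error. If it halves the later hazard, the differences are 12.19 − 12.01 = 0.18, 12.34 − 11.99 = 0.35 and 12.73 − 12.01 = 0.72 months.

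**Related loose ends.** The PFS formula has no term for the RT date, and the censoring reasons in Table 12 are only absence of a PFS event and withdrawal of consent. The RT rule is therefore not carried through 2.5.1.1 and its table either.

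**The case against.** Following responders to progression or death whatever treatment intervenes is a defensible choice, and 2.5.1.4 states it plainly. If PFS were changed to follow patients through RT, 2.5.1.4 would need no edit. This stands: neither rule is wrong alone. The fault is that the SAP uses both, on the same assessments, without a reason.

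Censoring at RT can also be informative if RT is given because progression is near. That stands as well, but PFS already carries this weakness.

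A reader might infer more than the text supports, in three ways.

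- **Systemic therapy.** One could say that duration ignores all other anti-cancer treatment while PFS censors for it. The PFS trigger is written as RT. Unless the looser second half of the sentence ("PFS will be censored at the date of anti-cancer treatment") is read as a wider rule, neither endpoint has a rule for non-protocol systemic treatment, and on that point they agree.
- **Best response and clinical benefit.** One could say that a response first seen after RT is credited to the palbociclib arm. The SAP does not say so. Section 2.5.1.3 refers to RECIST 1.1 and to further criteria that the SAP does not list; 2.5.2.3 refers to best response in evaluable patients. The assessment window is simply not stated, and the protocol, which is not at hand, may define it.
- **Bias between arms.** One could say that one arm gains duration it did not earn. Both arms receive palbociclib under identical endpoint rules, the SAP does not state whether investigators are blinded, and nothing in it shows that RT use or its effect differs by arm.

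**Conclusion.** The mismatch is real and follows from the two definitions with no assumed rates. A responder irradiated before progression is censored for PFS at RT and may have a later event for duration of response, and her duration exceeds her PFS time whenever progression falls later than the sum of her response and RT times.

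The practical size is probably small. On the assumed inputs the shift in an arm's median duration is about 0 to 0.7 months. The top of that range needs about 22% of responders to be irradiated before progression and RT to halve the later hazard. The SAP does not give the number of responders affected. Bias in the Table 17 comparison arises only if RT use or effect differs by arm. The point is confined to a secondary endpoint in responders; the primary PFS estimate and the sample size are untouched. It deserves correction because the result is incoherent within a patient and the remedy is cheap.

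**What to change.** 1. In 2.5.1.1, state whether the censoring trigger is RT only or any non-protocol anti-cancer treatment. Carry the rule into the PFS time formula and the censoring reasons in Table 12.
2. In 2.5.1.4, apply whatever rule PFS finally uses, so that a patient's duration of response cannot exceed her PFS time. If the difference is intended, give the reason instead.
3. Under Table 17, report by arm the number of responders who had such treatment before progression.

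The cost is SAP wording and a date cut on data already needed for PFS. The downside is possibly a few fewer duration events, and the same possible informative censoring that PFS already carries.
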